8.3 Effect Sizes

Effect size calculations supported the clinical relevance of the intervention (Cohen’s $d = 2.19$; Hedges’ $g = 2.16$), representing a very large effect.

8.4 Reliability

Reliability analysis demonstrated excellent internal consistency for the EHFSB-9, with Cronbach’s alpha values of .902 pre-intervention and .939 post-intervention.

8.5 Readmission Outcomes and Mann–Whitney U Test (Exploratory)

Of the 57 participants, 56 (98.2 percent) were not readmitted, and 1 participant (1.8 percent) experienced a heart failure-related readmission within 30 days. To assess whether readmission status influenced self-care improvement, a Mann–Whitney U test was conducted to compare EHFSB-9 improvement scores between readmitted and non-readmitted groups. Results indicated no statistically significant difference between groups (Mann–Whitney $U = 5.500$; Wilcoxon $W = 1601.500$; $Z = -1.370$; Asymptotic Sig. (2-tailed) = .171; Exact Sig. [2*(1-tailed Sig.)] = .211). Interpretation is limited by the extremely low number of readmissions ($n = 1$), which rendered the comparison underpowered.

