Impact of Discharge Teach-Back Education on Heart Failure Patients' Knowledge/Self-Care

Behaviors and 30-Day Readmissions

Statistical Analysis Plan (SAP)

NCT07280208

August 14, 2025

1. Introduction

This Statistical Analysis Plan (SAP) reflects the analyses that were performed for the completed project evaluating the impact of a structured discharge teach-back education intervention on heart failure self-care behaviors and 30-day heart failure-related readmissions.

2. Key Study Dates (Actual)

- Study Start Date: September 11, 2025 (Actual)
- Primary Completion Date: October 11, 2025 (Actual)
- Study Completion Date: November 10, 2025 (Actual)

3. Study Overview (as implemented)

- Design: Single-site quasi-experimental pre-test/post-test (within-subject).
- Intervention: Approximately 30-minute discharge teach-back education session.
- Measure: European Heart Failure Self-care Behavior Scale-9 (EHFScB-9).
- Follow-up: 30-day heart failure-related readmission determined via study-site electronic health record (EHR) review.
- Actual sample: N = 57 participants with complete pre- and post-intervention EHFScB-9 assessments.

4. Demographic Reporting

Due to the relatively small sample size and the potential risk of breach of confidentiality, detailed demographic data were not reported. However, all participants met the inclusion criteria and represented a clinically appropriate population for the intervention supporting the project's aim to improve transitional care and reduce readmissions.

5. Statistical Software and Significance Threshold

- Software: IBM SPSS Statistics, Version 29.0.1.0 (171).
- Statistical significance threshold: two-sided $p < 0.05$.

6. Outcomes and Scoring

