6.2 Readmission Outcome

Thirty-day heart failure-related readmission was coded as yes/no based on study-site EHR review.

7. Analytic Methods (Performed)

- Descriptive statistics summarized pre- and post-intervention EHFSB-9 scores.
- Paired-samples t-tests evaluated pre- to post-intervention changes across all nine EHFSB-9 domains/items.
- Because the number of readmissions was extremely low ($n = 1$), logistic regression was not feasible.
- A Mann–Whitney U test was used to compare EHFSB-9 improvement scores between the readmitted and non-readmitted groups (exploratory; underpowered).
- Scale reliability was assessed using Cronbach’s alpha (pre- and post-intervention).
- Effect sizes were calculated for the overall pre/post change using Cohen’s d and Hedges’ g .

8. Results Summary (Completed Study)

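### The exact Mann–Whitney p of .211 in SAP 8.5 comes from a no-ties distribution, although U = 5.5 with one readmitted participant proves a tie; on the printed doubling rule, with ties counted in the tail, it is .246 to .351

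*SAP*

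**What the plan says.** SAP 7 gives the method: "A Mann–Whitney U test was used to compare EHFSB-9 improvement scores between the readmitted and non-readmitted groups", qualified as "exploratory; underpowered". It does not say how ties are handled.

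SAP 8.5 gives the group sizes: "Of the 57 participants, 56 (98.2 percent) were not readmitted, and 1 participant (1.8 percent) experienced a heart failure-related readmission within 30 days". It then reports U = 5.500, W = 1601.500, Z = -1.370, "Asymptotic Sig. (2-tailed) = .171" and "Exact Sig. [2*(1-tailed Sig.)] = .211". It concludes that the groups do not differ significantly and says that a single readmission limits interpretation.

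SAP 5 sets a two-sided threshold of 0.05. Protocol 1.2 defines change as post minus pre, and Protocol 8.1 makes lower totals better, so improvement is a negative number. SAP 8.6 follows this coding: mean -18.52, median -20.00 and range 30.00 in the non-readmitted group.

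**The concern.** A reader who sees an asymptotic and an exact p side by side will trust the exact one more, above all with one participant in a group, where the normal approximation is weakest. Here the exact figure belongs to a distribution that cannot produce the observed statistic, while the Z next to it allows for the ties. Two treatments of the same data stand together with nothing to say so.

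The stake is small. This is the only exact inferential result for the exploratory objective, but no claim of a difference rests on it.

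**Working it through.** **Inputs.** From SAP 8.5: n1 = 1, n2 = 56, N = 57, U = 5.5, W = 1601.5, Z = -1.370, exact p = .211 defined as twice the one-tailed value. From SAP 8.6: non-readmitted mean -18.52, median -20.00, range 30.00. From SAP 8.2 and 8.3: overall mean difference 1.99, t = 16.542, Cohen's d = 2.19.

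**1. The plan's figure reproduced.** Without ties, U takes each of the values 0 to 56 with probability 1/57. P(U ≤ 5.5) = P(U ≤ 5) = 6/57, and 2 × 6/57 = .2105, which rounds to .211.

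**2. A tie is certain.**
- W = 56 × 57/2 + 5.5 = 1601.5 is the rank sum of the 56. All ranks sum to 57 × 58/2 = 1653, so the readmitted participant's rank is 1653 − 1601.5 = 51.5. A half-integer rank needs a tie with an odd number of others.
- Totals are sums of nine items on a 5-point scale, so changes are whole numbers. A range of 30 leaves at most 31 distinct values for 56 people.

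**3. The Z is tie-corrected.** Without ties, Z = (5.5 − 28)/√(56 × 58/12) = −22.5/16.452 = −1.368. The printed −1.370 needs a smaller variance, (56/12) × [58 − S/(57 × 56)], where S is the sum of t³ − t over all groups of t tied scores. Z rounds to −1.370 only if S lies between about 508 and 778. The asymptotic p does not discriminate: both versions of Z give .171.

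**4. Exact p with ties counted.** Let k others be tied with the readmitted participant and a others rank strictly above. Then a + k/2 = 5.5, the one-tailed p is (a + k + 1)/57, and it is doubled.

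| k | a | Tied group size | t³ − t | One-tailed | Doubled |
|---|---|---|---|---|---|
| 1 | 5 | 2 | 6 | 7/57 | .246 |
| 3 | 4 | 4 | 60 | 8/57 | .281 |
| 5 | 3 | 6 | 210 | 9/57 | .316 |
| 7 | 2 | 8 | 504 | 10/57 | .351 |
| 9 | 1 | 10 | 990 | excluded: 990 exceeds 778 | – |

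**5. Other conventions.**
- Doubled mid-p: 2 × (a + (k + 1)/2)/57 = 2 × 6/57 = .2105 for every k.
- Distance from the centre (rank at least 22.5 from 29): a single tied pair with no ties among the lowest ranks gives (7 + 6)/57 = .228. An enumeration of tie patterns compatible with Z and with at most 31 distinct values runs from 10/57 = .175 to 18/57 = .316.

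**6. Does U agree with the other results?**
- 16.542/√57 = 2.19, the stated d, so the 1.99 appears to rest on all 57 participants.
- If 1.99 is a mean per item, total improvement is 57 × 9 × 1.985 to 57 × 9 × 1.995, or 1018.3 to 1023.4 points.
- The 56 non-readmitted participants contribute 56 × 18.52 = 1037.1 points.
- The difference puts the readmitted participant at about +14 to +19, that is, worse after the session.
- With a median of −20 and a range of 30, no non-readmitted score can exceed −20 + 30 = +10. The readmitted participant would then be alone at rank 57, with U = 0, not tied at 51.5.

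**The case against.** The strongest reply is that the printed label fixes the doubling but says nothing about ties, so .211 is software output without a footnote and not an error. A doubled mid-p also equals .2105. That reply stands in part: a reader might infer that .211 is too small under any exact rule and that .246 is a general floor, and the documents do not support this. The distance rule falls on both sides of .211. But the SAP presents the figure as an exact doubled one-tailed probability, not as a mid-p, and on that definition the usual tail includes the tied participants.

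It can also be said that nothing depends on the number. This is right as to the conclusion: the SAP calls the test exploratory and underpowered, claims no difference, and prints the smaller asymptotic .171 in the same sentence. A reader might infer that the SAP materially overstates evidence for a difference; it does not.

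Last, a more precise p is of little use if U itself is wrong. This stands, and it sets the order of the fix.

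**Conclusion.** The point holds in a limited form and is minor. The value .211 is a no-ties figure for data that must contain ties at the readmitted participant's score. On the printed doubling rule with the inclusive tail, the exact p is .246 to .351, or 1.17 to 1.67 times the stated value (14/12 to 20/12). All versions, from .171 to .351, exceed 0.05.

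The range assumes that U and Z are correct as printed and that two-sided means twice the inclusive tail. A reader might go on to infer that U is proven wrong. The documents do not establish that: the conflict in step 6 depends on reading 1.99 as a per-item mean over all 57, which the SAP does not state. It is reason to check U, not to reject it.

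**What to change.** 1. Verify the readmitted participant's pre and post totals, change score and U against the source data. State in SAP 8.2 what the 1.99 averages over.
2. In SAP 8.5, replace .211 with the tie-aware exact p: 2 × (number of the 57, including the readmitted participant, whose post-minus-pre change is at or above that participant's) / 57. At or above on this coding means improved the same or less. The direction must be stated: counting scores at or below would take in at least 52 of 57 and give 2 × 52/57 = 1.82, which is not a probability. The formula assumes that rank 51.5 is confirmed and that the test used the coding of SAP 8.6.
3. Report the number tied, and state the two-sided convention and the handling of ties in SAP 7.
4. If .211 is kept, label it as not corrected for ties.

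The cost is one data check, one recount of 57 existing scores and a sentence or two of text. No new data are needed.

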8.6 Descriptive Improvement Scores (Non-readmitted Group)

For the non-readmitted group, the mean improvement score was -18.52 (SD = 7.26), with a median of -20.00 and a range of 30.00.

9. Limitations Relevant to Analysis

- Between-group comparisons by readmission status were underpowered due to a single readmission event ($n = 1$).
- Logistic regression modeling was not feasible because of sparse events.
- Readmissions were determined via study-site EHR review; readmissions to outside facilities may not have been captured.
